Primary outcome is systolic BP at 12-months, which is the major modifiable step to stroke event rate reduction. A secondary analysis will examine whether PACESETTER improved systolic BP by a clinically significant amount. Also apart from the 12 month primary outcome, we will also conduct a longitudinal comparisons of systolic BP in IG vs. SC over the course of followup evaluations. Participants will be given an appointment encounter solely for collecting evaluation data at the times listed in Figure 2. Trained assessors blinded to the randomization arm (with no contact with PACESETTER clinical team and instructed not to infer and probe on the intervention) will perform all study measurements. Potential mediator/moderators of risk factor control will also be collected. If a patient endorses severe depressive symptoms, patient will be referred to the appropriate medical professional.

Table 3. PACESETTER Outcomes and Mediators

Outcome Type	Measurements	Assessment Duration	Target Goal	Baseline	4 months	8 months	12 months
Primary	Systolic blood pressure ^{173,174}	<15 mins	< 130 mmHg	X	X	X	X
Secondary	Cardiovascular ED encounters and re-hospitalizations	<10 mins	Group differences	X	X	X	X
	Medication adherence ¹²⁵	<10 mins	Group differences	X	X	X	X
	Body mass index ¹²⁶	<5 mins	Group differences	X	X	X	X
	Self-management ^{127,128}	<10 mins	Group differences	X	X	X	X
Tertiary	Stroke, Myocardial infarction, Death	<10 mins	Group differences	N/A	X	X	X
Mediators	Age, education, income, depression, ^{129,130}	<5 mins	Group differences	X	N/A	N/A	N/A
	HTN/stroke Knowledge, ^{131,132} Health literacy, ^{133,134} disability, ^{135,136} and study site	<10 mins	Group differences	X	X	X	X
	Side effects, Adverse events (as reported)	<10 mins	Group differences	X	X	X	X

E.5.5.1. Physiological/Laboratory Measures

i. BP measurements: Three readings will be taken by trained assessors (if patient is unable to be seen in person, trained assessor will confirm the readings are taken correctly by patient either by verbal confirmation of procedures or visually watching the patient complete the BP measurements) using an automated BP monitor with the patient seated comfortably for 5 min prior to the measurements, following guidelines.^{137,138} Average of the last two BP readings will be used as the measure for each visit. Uncontrolled BP is defined as average clinic systolic BP ≥ 130 mm Hg or diastolic BP ≥ 90 mmHg per guidelines.¹³⁷

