iv. Chart extraction: Information extracted from the medical records will include medications and their dosages, biomarker measurements from clinic visits, and medical comorbidities.

E.5.5.3. Vascular Events (Specific Aim 3)

PACESETTER aims to collect any vascular events that take place while a patient is in the trial. This is being done to ensure that all events are captured in a timely fashion without any recollection biases. In order to do this, all participants & families will be urged to contact the RC as soon as any event that might be a CVD event

Program to Avoid Cerebrovascular Events through Systematic Electronic Tracking and Tailoring of an Eminent Risk-factor (PACESETTER)

has occurred. CVD events will include stroke, transient ischemic attack, or an acute coronary syndrome. Participants with potential CVD events will be evaluated by a study physician within 48 hours. If the history or the exam indicates that a stroke might have taken place, all clinical, laboratory & imaging data needed to confirm the event will be obtained by the RC & sent to a blinded physician adjudicator assigned to each site (see letters of support), for independent review. Final reports regarding the event will be sent to primary research site (MUSC) within 15 days. Participants with events will continue to be followed at scheduled intervals. These are study-specific steps the patient or caregiver will be asked to take once the CVD event has been addressed medically- ie, after the condition been treated and stabilized.

E.5.6. Statistical Considerations

E.5.6.1. Randomization

Once eligibility, consent & baseline data are confirmed, participants will be randomly assigned to PACESETTER intervention vs. usual care in a 1:1 allocation ratio, stratified by race (Black and White) & study site. An adaptive block randomization scheme will be developed & maintained by the lead study biostatistician. Once a patient is randomized he or she will be entered into the study and included in intent-to-treat analysis. The randomization assignment will be known to the project coordinator, and the statistician in charge of the randomization procedure, but not known to the research assistant who will be conducting participant follow-up assessments.

E.5.6.2. Power and Sample Justification

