Descriptive statistics will be computed for all study variables, including average follow-up time, retention rate, protocol deviations and violations, and will be compared by treatment group. We will use t-test for continuous variables and chi-square test for categorical variables to make comparisons between two groups and corresponding ANOVA for more than two groups. The primary analysis will be performed according to the principle of intention to treat. All outcomes will be modeled using regression analyses adjusted for baseline factors that show imbalance after randomization and compared to analysis that does not adjust for residual baseline differences.^{140,141} A nominal p value of 0.05 or less will be considered as statistically significant in the primary analysis. Analysis of covariance (ANCOVA) will be used to test the hypotheses in Aim 2 adjusting for baseline differences. Assessment of the fit of the models will be made using residual and diagnostic plots. We will employ longitudinal data methods (generalized linear mixed models [GLMM]),¹⁴² which account for correlation of outcomes due to repeated measurements and clustering by site and missing at random (MAR) data to study the change in outcomes over time between the two groups. In addition, to evaluate sensitivity of study conclusions to missing data, we will use multiple imputation methods to estimate single end-point outcome measures and carry out analyses on the complete data set using the MNAR statement in SAS 9.4. If we suspect violation of MAR then we will do additional sensitivity analysis.¹⁴³ Trajectory or change over time in BP and other related outcomes will be modeled via GLMM. Differences in time to recurrent events between the two groups will be compared using a log-rank test and a Cox proportional hazards (PH) model (we will test for the PH assumption) will be used to adjust for observed confounders. Since all participant data will be included in this analysis, participants missing outcome data will be censored at the last follow-up assessment time. Exploratory analyses will also be performed by sub-groups (e.g. age, gender, race) to determine if any differential efficacy exists. If statistically significant differences are found between IG and CG arms, we will conduct regression analyses further adjusted by variables selected based on a combination of clinical judgment and descriptive statistical findings comparing

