We have chosen a one year primary time point to balance maximizing study follow up with studying a clinically useful time period of adherence. Multiple tactics will be used to facilitate high IG patient retention including obtaining full contact information for patients, caregivers, and relatives at time of enrollment and updating every 3 months. Follow-up visits will be scheduled, whenever possible, on days subjects already have scheduled clinic visits or plan to visit the city. Research Nexus will be used as an additional location to complete study visits as needed. Phone call visits and televisits will be available if patients are unable to return to in-person visits. We will seek the guidance of PTF regarding all recruitment and retention strategies. Strategies will include regular telephone and mail contacts; in the CG these will not include material regarding stroke-related health care issues. Participants are receiving modest monies (\$50 per encounter, an additional \$50 for completing all study visits, and \$75 upon completion of KII interview) for being in the trial.

E.9.2. Individual Randomization

Program to Avoid Cerebrovascular Events through Systematic Electronic Tracking and Tailoring of an Eminent Risk-factor (PACESETTER)

We are randomizing patients instead of clusters, because it is the most statistically efficient method for showing efficacy and thus would require the smallest sample size.¹⁶⁵ Cluster randomization is appropriate when contamination threat is high,¹⁶⁶ but we believe the contamination threat is relatively small in this study.

E.9.3. Missing Data

Beyond attrition (wholly missing follow up assessments), we anticipate little missing data. Under the assumption of MAR, our analyses approach yields intent-to-treat parameter estimates that are consistent with what would be expected if there were no missing data. We will conduct secondary analyses of all hypotheses using only patients with complete data for comparison to the primary intent-to-treat analyses. The degree to which results differ (vs. not) between these two analyses will be reported. If the results differ, it will not be possible to determine which is “true.” Our position will be to emphasize the intent-to-treat results for both substantive and statistical (preservation of randomization) reasons.

E.9.4. Representativeness

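### E.9.3 claims consistent intention-to-treat estimates under MAR for the whole analysis, but the only model described for the primary 12-month SBP comparison is a single-visit regression whose handling of missing values is not stated

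*Combined protocol and SAP*

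**What the plan says.** - **Primary outcome (E.5.5).** "Primary outcome is systolic BP at 12-months, which is the major modifiable step to stroke event rate reduction". The repeated-measures comparison is additional: "Also apart from the 12 month primary outcome, we will also conduct a longitudinal comparisons of systolic BP in IG vs. SC".
- **Model for outcomes (E.5.7.1).** "All outcomes will be modeled using regression analyses adjusted for baseline factors that show imbalance after randomization", set beside a version without that adjustment. ANCOVA is named for Aim 2 only. The generalized linear mixed model (GLMM), described as accounting for MAR data, is given the task of studying change over time.
- **Imputation (E.5.7.1).** "to evaluate sensitivity of study conclusions to missing data, we will use multiple imputation methods to estimate single end-point outcome measures". Further sensitivity analysis is promised if MAR is doubted.
- **Analysis population (E.5.6.1).** "Once a patient is randomized he or she will be entered into the study and included in intent-to-treat analysis".
- **Missing data (E.9.3).** Under MAR, "our analyses approach yields intent-to-treat parameter estimates that are consistent with what would be expected if there were no missing data". Secondary analyses are then planned "using only patients with complete data for comparison to the primary intent-to-treat analyses", and the degree of difference is to be reported.
- **Expected loss (E.5.6.2).** 20%, with 200 enrolled to leave 160.

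Aim 1 in E.5 words the primary outcome as achievement of SBP control. That is a separate matter. This point concerns the 12-month SBP comparison in E.5.5, on which the sample size also rests.

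**The concern.** Consistency under MAR belongs to a particular estimator, not to a plan as a whole. A likelihood-based mixed model fitted to all visits has it, and so does imputation from the interim readings. A regression at one visit, fitted to those who have that visit, has it only if dropout depends on nothing beyond the terms in the regression. The plan gives both MAR-capable tools other jobs and then credits the property to everything.

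Dropout that differs by arm is plausible here. The intervention arm measures BP every 3 days with immediate feedback (E.5.3.1), while the control arm receives lifestyle messages (E.5.4). If intervention patients with high month-8 readings leave, the remaining intervention patients look better than the arm really is and the benefit is overstated. The reverse pattern understates it.

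The E.9.3 comparison would then give little warning. If the primary regression already rests on patients with a 12-month value, the complete-data analysis is largely the same model in the same patients, and agreement between them says almost nothing.

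**Working it through.** **Step 1. Figures from the plan (E.5.6.2).** Enrolment reproduces: 160 / (1 − 0.20) = 200, so about 40 patients would have no 12-month SBP. The effect of 0.5 SD is equated with 8.8 mm Hg, so SD = 8.8 / 0.5 = 17.6. The baseline to 12-month correlation is 0.8.

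**Step 2. Assumptions not in the plan.** The documents give no dropout mechanism. Assumed here: visits at 0, 4, 8 and 12 months; correlation 0.8 at all lags, or decaying with time to 0.8 between baseline and month 12; 20% missing month 12; dropout by a logistic model on observed month-8 SBP with odds ratio 2.7 per SD. Because dropout depends only on observed values, MAR holds exactly.

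**Step 3. Simulation.** 100 per arm, no treatment effect for the error rates, 2,000 to 3,000 trials per scenario. Ranges cover the two correlation patterns. Repeat runs moved the rejection rates by one or two percentage points.

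| Month-12 analysis | Dropout on SBP in one arm: bias, type I error | Opposite directions by arm: bias, type I error |
|---|---|---|
| Completers, baseline SBP in model | 0.5–0.8 mm Hg, 6–7% | 1.1–1.6 mm Hg, 10–16% |
| Completers, no baseline SBP | 2.4–2.9 mm Hg, 14–18% | 4.9–5.7 mm Hg, 43–57% |
| Likelihood estimate from all visits | about 0, 5% | about 0, 5–6% |

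Biases are absolute values; the sign follows the assumed direction of dropout. As a share of 8.8 mm Hg, the first row is 6–9% (0.5/8.8, 0.8/8.8) and 12–18% (1.1/8.8, 1.6/8.8). The second is 27–33% (2.4/8.8, 2.9/8.8) and 56–65% (4.9/8.8, 5.7/8.8).

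**Step 4. Check of the error rates by hand.** With 80 completers per arm:
- SE without baseline = 17.6 × √(2/80) = 2.78.
- SE with baseline = 17.6 × √(1 − 0.8²) × √(2/80) = 1.67.
- Type I error ≈ Φ(−1.96 + b/SE) + Φ(−1.96 − b/SE) for a bias b.

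With baseline, b = 0.5, 0.8, 1.1 and 1.6 give 6%, 8%, 10% and 16%. Without it, b = 2.4, 2.9, 4.9 and 5.7 give 14%, 18%, 42% and 54%. These agree closely with the simulation.

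**Step 5. Where the bias disappears.** With the same mechanism in both arms and no treatment effect, there is none. In large samples (400,000 patients per scenario) with a true effect of −8.8 mm Hg and the same dependence on SBP in both arms (odds ratio 2 to 4), it is −0.02 to +0.26 mm Hg with baseline SBP in the model and +0.21 to +0.99 without. If dropout depends on baseline SBP and arm only, the baseline-adjusted completer regression is unbiased within simulation error.

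**Step 6. Dependence on the SD.** E.5.6.2 also quotes a registry SD of 10.3. At that SD the biases in mm Hg shrink by 10.3 / 17.6 = 0.585 (0.5–0.8 becomes 0.3–0.5; 2.4–2.9 becomes 1.4–1.7). The error rates do not change, because bias and SE scale together.

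**The case against.** A reader might infer that the plan prescribes a completers-only primary analysis, and so is biased whenever MAR holds. The documents do not support either step. No section says that patients without a 12-month SBP are dropped. E.5.6.1 puts every randomised patient in the intention-to-treat analysis, and E.9.3 treats the complete-data analysis as something different from the primary one. The authors may have had the GLMM in mind when they wrote the MAR sentence. Step 5 also shows MAR mechanisms that leave a completer regression essentially unbiased.

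A reader might also infer that nothing planned could expose a problem. That is too strong: imputation of single end-points and the GLMM are both planned, and either could disagree with a completer regression. What is missing is a rule for which result then stands as primary.

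Three further objections have weight. E.5.6.2 assumes a baseline correlation of 0.8, so an analysis using baseline SBP was evidently contemplated; but E.5.7.1 brings baseline factors in only when imbalanced, so it is not assured. Control patients may also see their own BP: 65% of patients in the clinic survey in C.3 used home monitors. And E.9.3 describes attrition as wholly missing follow-up. If that means no follow-up visit at all, a mixed model has only the baseline reading to add and gains little over baseline-adjusted regression.

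What stands is that the MAR-capable methods are assigned elsewhere, and that treating end-point imputation as a sensitivity analysis implies the main end-point analysis is not imputed.

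**Conclusion.** The MAR statement in E.9.3 is broader than the plan supports. For the primary 12-month SBP comparison, neither the handling of missing values nor a MAR-valid estimator is specified, and the regression that is described can give a biased estimate while E.9.3 calls it consistent.

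The size depends on assumed dropout. With baseline SBP in the model it is modest for one-arm dropout and moderate for opposite dropout. The large errors need both arm-specific dropout and omission of baseline SBP. These figures rest on completer-only use, which is inferred, and on dropout driven by month-8 study SBP. If dropout followed home readings that are not in the model, strict MAR would fail for the mixed model too.

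This is more than a missing detail, because it affects the primary result and the plan already contains the data and model to avoid it. The change should be made, but it does not show that the trial's result will be wrong.

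**What to change.** In E.5.7.1, name the month-12 arm contrast from the planned mixed model as the primary SBP analysis: SBP at all follow-up visits, categorical visit, arm-by-visit interaction, baseline SBP prespecified whether or not it is imbalanced, and unstructured covariance. So that all randomised patients contribute, keep the baseline SBP of patients with no follow-up in the analysis, either by modelling baseline as one of the repeated measures with a common mean across arms or by imputing from baseline, month-4 and month-8 SBP.

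In E.9.3, limit the MAR sentence to that model and make the month-12 completer regression the secondary complete-data analysis, so that the comparison is between two different analyses.

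The cost is wording and slightly more modelling; the month-4 and month-8 readings and the GLMM are already planned. The gain over baseline-adjusted regression is small if most dropouts have no follow-up visit.

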This HIPAA compliant secure server file system will assist in keeping the site PI, designated healthcare team member and study staff updated via alert messages when needed based on patients' status and treatment plans. Subjects' data will be kept separate from any identifiers in MUSC's enterprise firewalled, encrypted, secure, data warehouse RDBMS (relational database management system) server. Their data are linked by an identified random subject ID#. The list with subject ID#s and all data parts are only accessed via an authenticated secure HTTPS access to the PI and biostatistician. The site PI and any designated healthcare provider/study staff identified within the PACESETTER team will also have a list that links a subject's ID# to their name and contact in order to follow-up on notifications of a BP range breach. Based upon care guidelines, ranges of acceptability will be set for the various parameters. If a patient exceeds any of these ranges the site PI or designated healthcare team member will receive automated text/email of a Patient Alert to check patient with ID #>>>. The site PIs, and designated healthcare team members will also receive summary charts of expert consensus BP management guidelines used by us in other studies.¹²⁴ PACESETTER site PIs or designated healthcare team members will receive weekly summary reports, using only patient ID #s

based upon their preference (eg., email; EHR with email reminder to view it). If a PACESETTER's mean BP exceeds thresholds (default markers BP >180/ 105 or <100/75 mmHg) during a session, the site PI (neurologist) or appropriate designee will receive an alert SMS or email, call the patient, and conduct the BP protocol again. If BP still exceeds thresholds, appropriate follow-up action will be initiated.

E.5.4. Standard Care (SC) Protocol

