Program to Avoid Cerebrovascular Events through Systematic Electronic Tracking and Tailoring of an Eminent Risk-factor (PACESETTER)

baseline characteristics between the IG and CG. These adjustments will help describe likely pathways by which the treatment influenced outcome. Additional analyses will assess patients' adherence to intervention and any secondary outcomes. We will adjust self reported measures for potential measurement error using standard techniques.¹⁴⁴

E.5.7.2. Management

Data will be captured via REDCap (a free, secure, web-based application) and overseen by a data management and analysis team comprising statisticians at MUSC. Data will be collected and sent electronically in password-encrypted files from the various sites to the team at MUSC. Secondary measures and demographics will be de-identified and sent to MUSC for double entry and comparison. Data will be reviewed on a bimonthly basis and issues will be communicated to the project coordinators. In particular outlying and inconsistent data values, as well as missing data, will be the targets of the data quality review.

E.6. Data Safety Monitoring Board (DSMB):

Given the minimal risk associated with the intervention, we will utilize an internal Data Safety Monitoring Board (DSMB) with the addition of one external member. The member extraneous to the project will be an experienced academic stroke attending neurologist based at an institution outside of South Carolina. The DSMB will meet twice per year to review study progress, e.g., recruitment, retention, drop out as well as possible adverse events.

E.7. PACESETTER (Specific Aim 4)

- Aim 4: To qualitatively explore provider effects of implementing the PACESETTER intervention vs. usual care, on the provider practice setting using focused ethnography.^{145,146}

E.7.1. Procedures

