‘Locally-grown’ scientists are needed to help understand the unique impact that race, culture, and environment have on the burden of cerebrovascular disease in SC and its environs. Well-trained stroke research scientists in the region would be more likely to show a predilection to work on topics or areas related to the unique challenges linked to stroke outcomes in the area. PACESETTER will incorporate talented post-doctoral scholars (nursing, psychology, public health) and stroke fellows at all participating academic institutions to join the research team as trainees as a way to introduce hands-on implementation research exposure early in their careers. Of note, [name] is the Editor-in-Chief of *eNeurologicalSci* (eNS), a peer-reviewed journal of the World Federation of Neurology (WFN) and Chair of the International Stroke Conference (ISC), the premier scientific stroke meeting in the world. He has directly mentored 35 post-doctorate scholars and junior faculty members on 150 peer reviewed publications, and is currently a mentor on a NIH career development award (K23AG044434). Early career investigators will be invited to participate in eNS editorial processes, as well submit their research work and engage in the multiple career development activities at ISC and WFN meetings.

E.13 Potential Risks

All precautions with data management and de-identification of records will be taken to protect the privacy of participants; however, as with any research study, there is always some risk of a breach in confidentiality. Additionally, participants may experience some emotional discomfort or anxiety when completing questionnaires about depression/anxiety or while measuring blood pressure. If needed, the study team will contact the correct professional that can provide assistance should a participant endorse symptoms of depression.

You may contact [name] [contact], or email [contact]

Program to Avoid Cerebrovascular Events through Systematic Electronic Tracking and
Tailoring of an Eminent Risk-factor (PACESETTER)

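### Low-BP harm is compared between arms without prompted items, while the arms are observed differently between visits; E.13 does not list low BP as a risk

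*Combined protocol and SAP*

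**What the plan says.** - **Risks (E.13).** Two are named. One is privacy: "there is always some risk of a breach in confidentiality". The other is that "participants may experience some emotional discomfort or anxiety when completing questionnaires about depression/anxiety or while measuring blood pressure". No physical effect of lowering BP is listed.
- **Alert (E.5.3.2).** If an intervention patient's session mean crosses the limits ("default markers BP >180/ 105 or <100/75 mmHg"), the site neurologist or a designee is alerted, calls the patient and repeats the measurement. "If BP still exceeds thresholds, appropriate follow-up action will be initiated". The same section has providers use the weekly reports for medication titration.
- **Harm data (E.5.5, Table 3).** The row "Side effects, Adverse events (as reported") is marked at baseline, 4, 8 and 12 months. It has a slot of under 10 minutes and the goal of group differences. It is not limited to one arm, and it appears to sit in the mediators block.
- **Control arm (E.5.4).** Patients receive lifestyle messages and a monthly call about contact details and hospitalizations. No home BP relay or BP alert is described.
- **DSMB (E.6).** The board is internal with one external member, a choice justified by "Given the minimal risk associated with the intervention". It meets twice a year to review progress, including "recruitment, retention, drop out as well as possible adverse events".

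**The concern.** The trial sets out to lower systolic BP through better adherence and through titration informed by home readings. The alert shows that the investigators expect some readings to be too low. A comparison of harms between arms is meaningful only if events are looked for in the same way in both.

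Here the visit question has no stated content, and what happens between visits differs by arm. A low reading or a dizzy spell may come to light in one arm through an alert call, and in the other through a hospitalization call or not at all. At stake is the trial's safety statement: an excess of low-BP harm could go unseen, or a difference could appear that reflects only how events were found.

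**Working it through.** The plan gives no safety figure to reproduce, so the check sets sections side by side and adds one count from the schedule.

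**1. Is low BP foreseeable on the plan's own terms?** Yes. E.5.3.2 sets the alert. In the pilot (C.4), mean systolic BP in the mHealth group fell by 153.9 − 136.3 = 17.6 mmHg, against 156.7 − 151.3 = 5.4 mmHg under standard care. Only eight patients had the mHealth program, so this shows the effect being sought and is not a reliable estimate of it. E.13 is silent on the matter.

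**2. Does another part of the plan capture low-BP harm?** The encounter codes in E.5.5.2 cover hypertension, coronary disease, dysrhythmia, heart failure and cerebrovascular disease. They do not name hypotension, fainting or falls. Event reporting in E.5.5.3 covers stroke, transient ischemic attack and acute coronary syndrome. The analysis section (E.5.7.1) describes no specific safety comparison. That leaves the Table 3 row, which has no event definition or symptom list in the available text.

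**3. How does observation compare?**

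| Route | Intervention | Control | Source |
|---|---|---|---|
| Post-baseline study visits, with BP and adverse events | 3 | 3 | E.5.5, Table 3 |
| Medication-count calls at months 2, 6 and 10 | 3 | 3 | E.5.5.2 |
| Home BP sessions that can trigger an alert, per year | about 243 | 0 | E.5.3.1, E.5.3.2, E.5.4 |
| Monthly calls about hospitalizations | not described | yes | E.5.4 |

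The session count is one measuring day in three, morning and evening: 365 / 3 = 121.7 days, and 121.7 × 2 = 243.3 sessions. It assumes full adherence for a year.

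**4. What follows for a comparison?** If the true event rate p is the same in both arms, and a share s_I of events is found in the intervention arm and s_C in control, the observed risk ratio is (p × s_I) / (p × s_C) = s_I / s_C. The true rate cancels. The ratio exceeds 1 if the alerts find more and falls below 1 if the monthly calls find more. The documents give neither share, so neither the direction nor the size can be fixed.

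**The case against.** A good deal of the plan points the other way.

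- **The DSMB.** A reader might infer that low BP lies outside the board's remit. E.6 does not support that, because possible adverse events are reviewed as a class. What stands is narrower: low BP is not named, and no review by arm is specified.
- **Collection.** A reader might also infer that harms are recorded only when patients volunteer them. Table 3 gives them a timed slot at every visit in both arms, and E.5.5 has blinded assessors make all study measurements. Staff may well ask, and the words in brackets may qualify adverse events alone. What stands is that the content of the question is not specified.
- **Size.** It is tempting to quote an inflation factor. Assumed detection of 75% against 60% gives 0.75 / 0.60 = 1.25, and swapping the arms gives 0.60 / 0.75 = 0.80. Either figure only restates the assumption. The alert also responds to a number, whereas symptoms can be noticed and reported in either arm.
- **Safety of patients.** The alert, call and repeat measurement are themselves a safeguard, and E.9.5 promises close monitoring of high-risk patients. The trial supplies no drug, and physicians in both arms get the same guideline charts. Nothing here shows that the intervention is unsafe or that the minimal-risk label is wrong.
- **Missing text.** Some pages, including consent pages, are not available, and E.10 plans an operations manual. Either might contain a symptom list or mention the risk. That would not change E.13 or Table 3 as written.

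**Conclusion.** The point holds as a modest improvement to how harms are measured. Visit-based collection exists in both arms but has no prompted low-BP or symptom items in the available text. Observation between visits differs by arm in ways that could bias a count up or down. E.13 omits a risk that E.5.3.2 foresees.

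The size of any bias cannot be derived from the documents. The one quantity that can be worked out is the contrast of about 243 alert-capable sessions a year with none, at full adherence. That describes opportunity to detect a low reading, not events missed. The primary systolic BP comparison is not touched. The conclusion rests on the alert and the monthly calls being confined to the arms for which they are described.

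**What to change.** - **Table 3.** Replace the as-reported wording with one short prompted list (for example dizziness, fainting, falls). The blinded assessors ask it in the same words in both arms at 4, 8 and 12 months. List it as a safety outcome.
- **E.5.7.1.** State that the arms are compared on these visit-based counts only. Tabulate separately any events found through the intervention-arm alerts or the control-arm monthly calls.
- **E.6.** Give the DSMB the counts by arm, with the number of study-visit BP readings below the plan's own alert limit. Say how the systolic and diastolic parts of that limit are read together. These readings are already taken, but three post-baseline visits will catch few transient episodes, so they supplement the symptom list and do not replace it.
- **E.13.** Add low BP to the stated risks.

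The cost is a few lines of text, slightly longer visits within the existing slot, and more minor events to record. Prompting does not remove every difference: patients are not blinded, and one who has had an alert call may recall symptoms more readily. No treatment rule or BP threshold is proposed.
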